1.0 Background

More than 78 million adults or $\approx 36\%$ of U.S. adults are obese with medical costs estimated to be \$210 billion annually. Bariatric surgery is the only modality that results in sustained weight loss along with reversal of type 2 diabetes mellitus (T2DM), improvements in cholesterol biosynthesis, lipoprotein metabolism, and decreased cardiovascular events.¹ In 2014, nearly 200,000 individuals in the US underwent bariatric surgery and each year the number increases by 22%.

We² and others, ^{3,4} showed that obesity results in an increased sympathetic (SNS) activity decreased parasympathetic (PNS) activity and altered baroreflex sensitivity. Previous studies showed that bariatric surgery significantly reduces sympathetic activity. Vertical sleeve gastrectomy (VSG) decreases SNS as measured by direct sympathetic nerve recording at 6 and 12 months post-surgery.⁵ Roux-en-Y gastric bypass (RYGB), the most common bariatric procedure, also reduces SNS at 3 and 6 months post-surgery.⁶ The mechanism underlying these sympatholytic actions are not completely understood but were found to be associated with a decrease in visceral fat⁷ and leptin levels.⁵ Regardless of the mechanism(s) involved, the reduction in SNS activity induces a decline in blood pressure in post-bariatric surgery patients⁸, which can have in some cases deleterious effects. Importantly, a previous study showed mild orthostatic hypotension in otherwise asymptomatic post-bariatric subjects.⁹

Recent retrospective studies and case series reported an orthostatic intolerance (OI) syndrome characterized by symptoms of cerebral hypo perfusion upon standing associated with pre-syncope and recurrent syncope.¹⁰⁻¹⁴ Our recent preliminary data support these findings; in our center, we performed 4,906 bariatric procedures (78.4% RYGB and 19.7% VSG) in the past 20 years. Patient's follow up after surgery is reduced to \approx 15% at 5 years. Despite this attrition, 741 post-bariatric surgery patients, reported symptoms of OI. Chart review showed that 98 (13.2%) of these patients, progressed to chronic OI unexplained by anti-hypertensive use, vitamin deficiency or fluid loss. In 17 cases, the OI is so disabling that patients had to be treated with pressor agents such as midodrine and fludrocortisone.

Normally, after assuming the upright position gravitational forces shift about 700 ml of blood volume to the lower part of the body, particularly the splanchnic circulation;¹⁵ to compensate for the decrease in venous return, the SNS is maximally activated to induce vasoconstriction. We, therefore, hypothesize that the decrease in SNS activity in post-bariatric subjects results in insufficient vasoconstriction upon standing, causing patients to have OI.

2.0 Specific Aims

Specific Aim 1: To test the hypothesis that bariatric surgery (RYGB and VSG) impairs sympathetic vasoconstrictor activity and lead to the development of orthostatic intolerance independent of weight changes.

Specific Aim 2: To test the hypothesis that potentiating sympathetic vasoconstrictor activity will reverse the impaired orthostatic tolerance post-bariatric surgery.

3.0 Inclusion/Exclusion Criteria

We will recruit obese patients that will undergo bariatric surgery and medical weight loss from the Vanderbilt Center for Weight Loss (VWL). We will study three groups before and after 10% weight loss (15 RYGB, 15 VSG, and 15 medical weight loss).

Inclusion criteria

- Obese subjects that will undergo bariatric surgery or medical weight loss.
- Age 18-65 years
- BMI >35 kg/m²
- Weight < 400 lbs

Exclusion criteria:

Subjects presenting with any of the following will not be included in the study:

- Diabetes type 1
- Use of an alpha blockers, clonidine, beta-blockers.
- Pregnancy or breast-feeding. Women of childbearing potential will be required to have undergone tubal ligation or to be using an oral contraceptive or barrier methods of birth control.
- The use of any strong CYP2D6 inhibitor (e.g., fluoxetine, paroxetine, quinidine, tipranavir).
- Use of selective NET inhibitors.
- Use of monoamine oxidase inhibitors.
- Cardiovascular disease such as myocardial infarction within six months prior to the study, presence of angina pectoris, significant arrhythmia, congestive heart failure (left ventricular hypertrophy acceptable), deep vein thrombosis, pulmonary embolism, second or third degree heart block, mitral valve stenosis, aortic stenosis or hypertrophic cardiomyopathy
- History of serious neurologic disease such as cerebral hemorrhage, stroke, or transient ischemic attack
- Hematocrit < 34%
- Any underlying or acute disease requiring regular medication which could possibly pose a threat to the subject or make implementation of the protocol or interpretation of the study results difficult
- Mental conditions rendering a subject unable to understand the nature, scope and possible consequences of the study
- Inability to comply with the protocol, e.g., uncooperative attitude, inability to return for follow-up visits, unlikelihood of completing the study, and investigator discretion

4.0 Enrollment/Randomization

Recruitment and informed consent:

We will recruit obese patients that will undergo bariatric surgery and medical weight loss from the Vanderbilt Center for Weight Loss (VWL). The VWL clinic is the largest bariatric surgery facility in Tennessee and annually performs \approx 500 bariatric surgeries. We may also recruit persons willing to participate in the Jenny Craig weightloss program for 6 weeks. We will use research match and subject locator as well as an online pre-screening survey. We will use printed consent and e-consent to consent the subjects, for the two, parallel-arm, placebo-controlled portion of the study. We will randomize 1:1 to either placebo vs. the NE-transporter inhibitor, atomoxetine, at doses of 0.5 mg/kg/day.

5.0 Study Procedures

Pre-screening survey: Potential participants may choose to complete a pre-screening survey that will better evaluate their eligibility. Subjects may complete the survey on their own or while in clinic.

Screening evaluation: Patient will be consented by phone. We will review the pre-surgical evaluation to assess for inclusion/exclusion criteria and we will invite to complete additional visits in the center for surgical weight loss or the autonomic cardiovascular suite.

Visit 1: Baseline (pre-surgery, RYGB/VSG) or pre-hypocaloric diet (medical weight loss).

Visit 2: After 10% weight loss. The time is variable (RYGB/VSG= 10-12 days; medical weight loss group= \sim 30-40 days).

Visit 3 (only for RYGB and VSG groups): 3-months after the bariatric procedure.

Visit 4 (only for RYGB and VSG groups): After 3-days on stable doses of Strattera (atomoxetine) vs. matching placebo. For the two, parallel-arm, placebo-controlled portion of the study. We will randomize 1:1 to either placebo vs. the NE-transporter inhibitor, Strattera (atomoxetine), at doses of 0.5 mg/kg/day.

Visits 1-4 specific procedures:

In supine position, we will measure: 1) plasma volume assessment; 2) continuous beat-to-beat blood pressure, and heart rate monitoring; 3) muscle sympathetic nerve activity (MSNA) with microneurography (at the physician's descretion), 4) blood volume assessment; and 5) supine plasma catecholamines and metabolites.^{2, 16} We will assess orthostatic tolerance using tilt table testing.^{17, 18} We will perform a 60° head-up tilt (HUT) for 30 min until pre-syncope (defined as systolic BP (SBP, mm Hg) <80 or SBP>90 and pre-syncopal symptoms (nausea, lightheadedness, dizziness).¹⁹ We will repeat plasma catecholamines at the end of the 30 min HUT and hemodynamic measurements throughout the HUT. The supine and 60° HUT plasma catecholamines will provide information on orthostatic-induced sympathetic neuro-hormonal activation. We will use the ratio dihydoxyphenylglycol (DHPG) to NE as the biomarker for NET inhibition as we previously reported.²⁰ We will repeat the serum pregnancy test (if applicable).

We will wait 24 hours to perform visits 1-4 if the patient has received IV fluids for clinical care.

Our primary endpoint (orthostatic tolerance, OT) is defined as the time between the start of the 30° HUT until pre-syncope

Justification for Strattera dose and frequency. We selected a weight-adjusted dose (0.5 mg/kg/day or equivalent to 40 mg/day) because body weight has a significant impact on Strattera pharmacokinetics.²¹ The weight-adjusted dose will provide comparable exposure between patients of different body sizes, which is of particular importance in the obese post-bariatric population. The $T\frac{1}{2}$ of atomoxetine is 5.6 hours,²¹ hence we will study subjects after 3-day treatment to achieve stable concentrations. Specific procedures for visit 4 will be performed two hour after intake of blinded study medication. Atomoxetine reaches maximum plasma concentration within two hours after administration.

The PI ([name]) holds an IND (117394) for the use of Strattera (atomoxetine) for indication other than attention deficit hyperactivity disorder.

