6.0 Risks

Blood Draws: Subjects may experience discomfort, bruising, and/or bleeding, or infection at the needle insertion site after a blood draw. Rarely, some people faint. Frequent blood sampling may cause anemia. We will exclude subjects with hematocrit <34%

12-hour fast: Participants may experience hunger during a 12-hr fast, however this is a standard requirement by clinicians for accurate blood testing.

Study medication: NET blockade such as Strattera can cause severe hypertension when taken together with monoamine oxidase inhibitors. For this reason, subjects will be asked to wear a medical alert bracelet stating that they should not be given a monoamine oxidase inhibitor without first contacting the PI. Common (>10%) side effects associated with Strattera are headaches (2% to 19%), insomnia (2% to

15%), somnolence (4% to 11%), xerostomia (21%), nausea (7% to 21%), abdominal pain (7% to 18%), appetite decrease (11% to 16%), and vomiting (3% to 11%). Research subjects will be informed of all the potential side effects associated with the drug. All potential adverse events will be ranked according to severity and will be reported according to the data and safety-monitoring plan described below.

Strattera has been associated with suicidal ideation in children. The frequency of suicidal ideation is 0.37% (5/1,357) based on a recent meta-analysis. Because subjects will only receive acute doses of Strattera, the risk of suicidal ideation is minimal.

Intravenous Cather Insertion:

Inserting a plastic catheter into the vein may cause a brief amount of pain and possibly a small bruise at the site, but will allow us to draw blood without repeated sticks throughout the study. It is also possible to develop an infection at the location of the catheter. It is uncomfortable to have the intravenous catheter in place for any length of time because it causes discomfort when the patient moves their arm.

Tilt table testing:

The potential risks associated with this procedure are: 1) subjects **may** experience low back pain after lying down on the tilt table test; 2) there is a risk of syncope and/or low blood pressure. These events, however are expected considering that the procedure intend to cause evaluate orthostatic intolerance. We have specific rules for when to stop the procedure and move subjects to recumbent position (pre-syncope defined as SBP<80 mmHg or SBP>90 mmHg and pre-syncopal symptoms (nausea, lightheadedness, dizziness).

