8.0 Study Withdrawal/Discontinuation

Criteria for study withdrawal/discontinuation

- Drug-related toxicity
- Requirement for prohibited concomitant medications (see exclusion criteria)
- Pregnancy
- Request by subject to terminate treatment
- Clinical reasons believed to be life threatening by the physician, even if not addressed on the potential risk section

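### The pre-syncope rule that stops the tilt and ends the primary endpoint leaves out symptoms that first appear at SBP 80 to 90 mm Hg

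*Combined protocol and SAP*

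**What the plan says.** Section 5.0 (Visits 1-4 specific procedures) describes a head-up tilt of 30 minutes that runs until pre-syncope, "defined as systolic BP (SBP, mm Hg) <80 or SBP>90 and pre-syncopal symptoms (nausea, lightheadedness, dizziness". The same section then sets the endpoint: "Our primary endpoint (orthostatic tolerance, OT) is defined as the time between the start of the" tilt and pre-syncope. Section 9.0 (Data Analysis Plan) makes OT the primary comparison in both aims.

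Section 6.0 (Tilt table testing) uses the rule for safety. It states "We have specific rules for when to stop the procedure and move subjects to recumbent position" and gives the rule as "pre-syncope defined as SBP<80 mmHg or SBP>90 mmHg and pre-syncopal symptoms (nausea, lightheadedness, dizziness".

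The two statements are formatted differently but carry the same thresholds and the same directions. Nothing elsewhere in the document restates or corrects them.

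Two other provisions bear on the point. Section 5.0 plans pressure recording during the tilt: "We will repeat plasma catecholamines at the end of the 30 min HUT and hemodynamic measurements throughout the HUT". Section 8.0 allows withdrawal at the participant's request or for "Clinical reasons believed to be life threatening by the physician, even if not addressed on the potential risk section".

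**The concern.** One inequality does two jobs. It tells staff when to lay a participant flat, and it stops the clock on the primary endpoint. As written, it accepts pre-syncopal symptoms at a normal pressure but not the same symptoms at 85 mm Hg. The documents offer no rationale for such a hole.

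Two things are at stake. Read literally, the rule does not call for ending the tilt of a symptomatic participant with low pressure. That participant's OT is also longer than it would be if the symptoms counted. In addition, staff who notice the gap must choose their own repair, and the plausible repairs give different OT for the same tilt.

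**Working it through.** **Inputs.** The rule in Sections 5.0 and 6.0; its use as the endpoint event (5.0) and as the tilt stop (6.0); the group sizes (3.0) and visit schedule (5.0). The plan gives no figure for how the rule performs, so there is none to reproduce. The Section 9.0 sample size does reproduce: for 18.9 versus 27.5 with SD 7 and n = 15 per group, power is 90.1% by the noncentral t, against the stated 90%. It is not in dispute.

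**Step 1: the two possible bracketings.**
- Reading A: (SBP <80) or (SBP >90 and symptoms).
- Reading B: (SBP <80 or SBP >90) and symptoms.

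**Step 2: truth table, with two candidate corrections.**

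| SBP (mm Hg) | Symptoms | A | B | SBP <80, or symptoms at any SBP | SBP <80, or SBP ≤90 with symptoms |
|---|---|---|---|---|---|
| 75 | no | met | not met | met | met |
| 75 | yes | met | met | met | met |
| 80 | yes | not met | not met | met | met |
| 85 | yes | not met | not met | met | met |
| 90 | yes | not met | not met | met | met |
| 91 | yes | met | met | met | not met |
| 130 | yes | met | met | met | not met |

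**Step 3: count within the gap.** There are 90 − 80 + 1 = 11 whole-number readings. With symptoms present, the written rule fails at 11 of 11 under A and 11 of 11 under B. Either correction in the table fails at 0 of 11. A strict *SBP <90 with symptoms* would still fail at 1 of 11 (exactly 90).

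**Step 4: other rows.** A and B disagree at SBP 75 without symptoms, so the text does not settle whether a pressure below 80 is enough alone. The two corrections disagree at 91 and 130 with symptoms: the first keeps stops that the current text allows, the second removes them.

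**Step 5: follow a tilt over time.** If symptoms begin while SBP is above 90, both readings are met at once and the tilt ends before the gap is reached. The gap therefore matters only when symptoms first appear with SBP already at 80 to 90. It closes when SBP drops below 80, when SBP rises above 90 with symptoms, or when the 30 minutes run out.

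**Step 6: where the rule applies.** Section 3.0: "We will study three groups before and after 10% weight loss (15 RYGB, 15 VSG, and 15 medical weight loss"). Visits 3 and 4 are for the surgical groups only (for example "Visit 4 (only for RYGB and VSG groups")). If everyone completes, 45 × 2 + 30 × 2 = 150 tilts come under the rule, 30 of them at the randomized visit 4. This counts tilts governed by the rule, not tilts affected by the gap.

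**The case against.** The strongest reply is that the consequence is narrow and its size unknown. That stands. Symptoms starting above 90 already stop the tilt, so only first onset at 80 to 90 is affected, and only until one of the three exits in Step 5. The documents give no frequency of such onsets and no rate of pressure fall.

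A second reply is that participants are protected anyway. Section 6.0 says when to stop, not that a tilt may be stopped only then, and Section 8.0 lets a physician or participant withdraw. This limits the safety consequence. But Section 8.0 concerns leaving the study; it sets no tilt threshold and does not say when OT ends.

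Three stronger readings are tempting and are not supported:
- A reader might infer that the second sign is a slip for less than 90. The same direction appears in both sections, and Section 1.0 describes orthostatic intolerance by symptoms, so counting symptoms at preserved pressure may have been intended. The definition cites a reference that cannot be consulted here. The intended threshold stays open.
- A reader might infer that OT is generally overstated, that the arms are biased against each other, or that power is lost. Nothing in the documents allows any of these to be shown.
- A reader might infer that staff are obliged to keep symptomatic participants upright. No text says so; the point is what the rule calls for when applied literally.

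**Conclusion.** The rule is wrong as written in both places where it operates. On either bracketing, pre-syncopal symptoms that first appear at SBP 80 to 90 inclusive neither trigger the tilt stop nor end OT, although the same symptoms at a higher pressure do both. Whether SBP below 80 without symptoms counts is also left open.

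The logical gap is certain from the text; it assumes only that the rule is applied literally. The number of tilts affected and the effect on OT cannot be estimated, and none is claimed. If staff already stop for symptoms in this band, only the text needs changing. It still needs changing, because it defines a safety stop and the primary endpoint of both aims.

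**What to change.** Correct the rule identically in Sections 5.0 and 6.0, with the investigator confirming the intent.

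- **Default:** *SBP <80, or pre-syncopal symptoms at any SBP*. This closes the gap, keeps every symptomatic stop now allowed, and makes clear that SBP below 80 counts without symptoms.
- **Alternative:** *SBP <80, or SBP ≤90 with pre-syncopal symptoms*. Use this only if the investigator confirms that symptoms above 90 were never meant to count, because it removes stops that the current text permits.

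The cost is one inequality corrected in two sections. No test, visit or sample size changes. Recording the reason for stopping at each tilt is optional and not needed for the correction; pressure at the stop should already be available from the planned measurements during the tilt.

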6.0 Risks

Blood Draws: Subjects may experience discomfort, bruising, and/or bleeding, or infection at the needle insertion site after a blood draw. Rarely, some people faint. Frequent blood sampling may cause anemia. We will exclude subjects with hematocrit <34%

12-hour fast: Participants may experience hunger during a 12-hr fast, however this is a standard requirement by clinicians for accurate blood testing.

Study medication: NET blockade such as Strattera can cause severe hypertension when taken together with monoamine oxidase inhibitors. For this reason, subjects will be asked to wear a medical alert bracelet stating that they should not be given a monoamine oxidase inhibitor without first contacting the PI. Common (>10%) side effects associated with Strattera are headaches (2% to 19%), insomnia (2% to

15%), somnolence (4% to 11%), xerostomia (21%), nausea (7% to 21%), abdominal pain (7% to 18%), appetite decrease (11% to 16%), and vomiting (3% to 11%). Research subjects will be informed of all the potential side effects associated with the drug. All potential adverse events will be ranked according to severity and will be reported according to the data and safety-monitoring plan described below.

Strattera has been associated with suicidal ideation in children. The frequency of suicidal ideation is 0.37% (5/1,357) based on a recent meta-analysis. Because subjects will only receive acute doses of Strattera, the risk of suicidal ideation is minimal.

Intravenous Cather Insertion:

Inserting a plastic catheter into the vein may cause a brief amount of pain and possibly a small bruise at the site, but will allow us to draw blood without repeated sticks throughout the study. It is also possible to develop an infection at the location of the catheter. It is uncomfortable to have the intravenous catheter in place for any length of time because it causes discomfort when the patient moves their arm.

Tilt table testing:

The potential risks associated with this procedure are: 1) subjects **may** experience low back pain after lying down on the tilt table test; 2) there is a risk of syncope and/or low blood pressure. These events, however are expected considering that the procedure intend to cause evaluate orthostatic intolerance. We have specific rules for when to stop the procedure and move subjects to recumbent position (pre-syncope defined as SBP<80 mmHg or SBP>90 mmHg and pre-syncopal symptoms (nausea, lightheadedness, dizziness).

Muscle Sympathetic Nerve Activity:

The potential risk associated with this procedure are: 1) numbress sensation and/or pain in the area of nerve stimulation and/or needle insertion; 2) discomfort when the patient moves his/her leg; 2) potential risk of infection in the site of needle insertion. We will minimize these potential risks by applying sterile technique for needle insertion. [name] has significant experience in the use of this technique and will choose which subjects will have the procedure.

Blood volume assessment:

As part of this research study, participants will receive a small amount of radioactive substance called Iodine-131. Iodinated I-131 albumin (Volumex[®]), injected intravenously for determination of total plasma volume, is a radiopharmaceutical and, as such, requires that care be taken to ensure minimum radiation exposure consistent with proper patient management. Each 1 ml dose of Volumex[®] contains 25 microcuries in a pre-filled injection kit. This radioactive substance will expose participants to a small amount of radiation (x-rays). The radiation dose that they will receive from each procedure is about the same amount that they would receive over a period of four months from natural background radiation. Natural background radiation comes from naturally occurring radioactive material that is present in everyone's body, from outer space (cosmic radiation), and from naturally occurring radioactive material in soil, rocks, and building materials. This procedure will be performed a maximum of two times at an interval of at least several weeks. I-131 tagged human albumin is a human blood product. This product has been screened and heat-treated for at least 10 hours at 60°C. Experts demonstrated that this treatment kills the encapsulated viruses (like HIV and Hepatitis C). Recent studies have shown that the risk of getting a disease from human blood products such as this is extremely small. However, some individuals may not want to receive human blood products for religious or other ethical concerns.

Breach of Confidentiality:

In the event of a security breach, confidential information may be stolen. We have strong security procedures in place to minimize the possibility of a breach. Although we cannot provide a 100%

guarantee that the participant's data will be safe, our procedures minimize the chance that a breach would take place.

There is no benefit of the proposed research to the subjects per se.

7.0 Reporting of Adverse Events (AEs) or Unanticipated Problems involving Risk to Participants or Others

All protocols will be reviewed and approved by the Vanderbilt Institutional Review Board (IRB) before enrolling any subject. Any untoward medical event will be classified as an AE, regardless of its causal relationship with the study. The PI will be responsible for ensuring both data integrity and for ensuring that study participants are safely cared for, and that all AEs are noted, followed, and reported to the IRB, the DSMO, and the FDA.

We will use the Guidance for Industry and Investigators for safety reported requirements for INDs and BA/BE studies published in the FDA website:

http://www.fda.gov/downloads/Drugs/GuidanceComplianceRegulatoryInformation/Guidances/U CM227351.pdf

Definitions:

Adverse event (AE) means any untoward medical occurrence associated with the use of a drug in humans, whether or not consider drug related. Suspected AE means any AE for which there is reasonable possibility that the drug caused the AE; "reasonable possibility" means there is evidence to suggest a causal relationship between the drug and the AE.

An AE will be considered unexpected if it is not listed in the investigator brochure.

Serious AE means any AE that: a) results in death, b) is life-threatening, c) requires inpatient hospitalization or prolongation of existing hospitalization, d) results in persistent or significant disability or incapacity, e) is a congenital anomaly or birth defect.

Serious adverse events will be reported to the Chairman of the Data and Safety Monitoring Board (DSMB), the IRB, and the FDA no later than 7 calendar days after the PI's initial receipt of the information.

Suspected AE interpretable as single case (uncommon and strongly associated with drug exposure) will be reported to the FDA within 15 days from initial receipt.

Non-serious, unexpected adverse events will be reported to the IRB at the time of the annual continuing review.

The Data Safety Monitoring Officer (DSMO), [name], Director of the Vanderbilt Hypertension Service, a patient-oriented investigator with experience in clinical research, will serve as DSMO and consultant for this grant. We will provide annual reports to the IRB and the DSMO regarding recruitment, safety reporting, data quality, and efficacy.

Incidents of non-compliance with the protocol will be reported at the time of continuing review.

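### Section 5 lists plasma and blood volume at four visits for surgical participants, but Section 6 allows I-131 albumin, the only method named, at most twice

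*Combined protocol and SAP*

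**What the plan says.** Section 5.0 (Study Procedures) has one procedure list, headed "Visits 1-4 specific procedures". Plasma volume is the first item: "In supine position, we will measure: 1) plasma volume assessment; 2) continuous beat-to-beat blood pressure, and heart rate monitoring". Blood volume is the fourth: "4) blood volume assessment; and 5) supine plasma catecholamines and metabolites". Neither is restricted to certain visits. One item in the list does carry a qualifier: "muscle sympathetic nerve activity (MSNA) with microneurography (at the physician's descretion".

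The same section limits the last two visits to the surgical groups. The third visit is a timed follow-up: "Visit 3 (only for RYGB and VSG groups): 3-months after the bariatric procedure". The fourth, which tests the study drug against placebo, carries the same restriction: "Visit 4 (only for RYGB and VSG groups): After 3-days on stable doses of Strattera (atomoxetine) vs. matching placebo".

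Section 6.0 (Risks), under its blood volume entry, describes I-131 albumin (Volumex), "injected intravenously for determination of total plasma volume". It gives 25 microcuries per 1 ml dose and equates each procedure with about four months of background radiation. It then sets the limit: "This procedure will be performed a maximum of two times at an interval of at least several weeks".

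**The concern.** The schedule and the cap imply different numbers of procedures for surgical participants. If I-131 albumin is the method, carrying out the Section 5.0 list at every visit goes past the Section 6.0 maximum, and keeping to the maximum leaves listed assessments undone.

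Two things are at stake. The first is exposure to a radiopharmaceutical in a study that, by the end of Section 6.0, offers participants no benefit of their own. The second is which visits have volume data. Two measurements give one within-person change, so they cannot cover both the change with weight loss (Visit 1 to Visit 2) and the change on study drug (Visit 3 to Visit 4). If the choice is left to staff, surgical participants may be measured at different visits from one another, or may lack the Visit 2 value that the medical group has.

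**Working it through.** No power or sample-size formula applies. The check is a count of listed assessments against the cap.

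**Inputs**

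- Visits with volume in the procedure list: 1 to 4 (Section 5.0).
- Visits 3 and 4: RYGB and VSG only (Section 5.0).
- Planned participants: 15 RYGB, 15 VSG, 15 medical weight loss (Sections 3.0 and 9.0).
- Maximum I-131 procedures per participant: 2 (Section 6.0).
- Activity per dose: 25 microcuries. Background equivalent per procedure: about 4 months (Section 6.0).
- Assumption: one procedure is one 1 ml dose, and it serves both the plasma and the blood volume item at a visit.

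**Step 1. Can the cap of 2 be recovered from the schedule?** Excess = listed visits − cap.

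| Group | Listed visits per participant | Cap | Excess | Group total, listed | Group total, cap |
|---|---|---|---|---|---|
| RYGB | 4 | 2 | 4 − 2 = 2 | 15 × 4 = 60 | 15 × 2 = 30 |
| VSG | 4 | 2 | 4 − 2 = 2 | 15 × 4 = 60 | 15 × 2 = 30 |
| Medical weight loss | 2 | 2 | 2 − 2 = 0 | 15 × 2 = 30 | 15 × 2 = 30 |

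The cap matches the schedule in the medical group and does not in either surgical group. Over the 30 surgical participants, 60 + 60 = 120 visit-level assessments are listed and 30 + 30 = 60 are allowed.

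**Step 2. Data under the cap.** With I-131 alone, at most 2/4 = 50% of listed surgical visits can have volume data. No section available for review assigns the procedures to visits.

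**Step 3. Exposure.** These totals are derived; the protocol gives only the per-dose and per-procedure figures.

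- Cap kept: 2 × 25 = 50 microcuries, or about 2 × 4 = 8 months of background.
- Cap ignored, one injection at each of four visits: 4 × 25 = 100 microcuries, or about 4 × 4 = 16 months. This is a hypothetical breach, not an exposure that the protocol permits.

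**Step 4. Spacing.** The requirement that procedures be several weeks apart is not a separate conflict, because two procedures can be placed to satisfy it. Purely as an illustration, Visits 1 and 3 are at least three months apart in the surgical groups. The gaps from Visit 1 to surgery and from Visit 3 to Visit 4 are not given, so the number of pairs of visits that meet the limit cannot be worked out.

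**The case against.** The best defence is that the conflict is conditional. Section 5.0 names no method and lists plasma volume and blood volume separately, while the cap governs the I-131 procedure and not every volume assessment. Section 6.0 is a risk section, so its silence on a second method proves little: beat-to-beat blood pressure and heart rate monitoring has no risk entry either. Section 5.0 is also a loose composite. It includes a biomarker of norepinephrine transporter inhibition in the common list, although study drug is given only before Visit 4. A reader could fairly take the specific cap as limiting the general list. The consent pages, which were not available for review, may assign the procedures to visits.

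Part of this stands. A second, unnamed method is possible, the consent text may contain more, and the 50 microcuries is derived rather than stated. The 100 microcuries requires ignoring an explicit limit.

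None of it removes the mismatch. No section available for review names another method, and the two items do not divide neatly by method, because the entry headed as blood volume describes a determination of plasma volume. Where the protocol intends an exception in the list, it marks one, for microneurography. If the cap does override the list, Section 5.0 still lists assessments at two surgical visits that the only named method cannot supply, and the text does not say which two.

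**Conclusion.** The concern holds. Each of the 30 planned surgical participants has four visits with listed volume assessments against a maximum of two procedures by the only named method. The medical weight loss group is consistent at two against two. Confidence is high for the count. It does not extend to any actual exposure, and it depends on no unstated second method being in use at some visits.

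The inconsistency should be corrected because following Section 5.0 as written with I-131 would breach a stated limit on radiation exposure. Its reach is narrow. Section 9.0 names orthostatic tolerance as the primary endpoint and hemodynamics, catecholamines and sympathetic nerve activity as secondary, so neither the sample size nor the primary analysis is affected.

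**What to change.** Reconcile Sections 5.0 and 6.0. For each group, state the visits at which plasma volume and blood volume are assessed and the method used at each. The number and spacing of I-131 administrations, and the radiation exposure described, should then agree in both sections and in the consent text. If a second method is intended, name it. Which passage governs is for the investigator and the radiation safety reviewers to decide.

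The cost is an edit to two sections, and to the consent text if it differs. It needs no additional participants and no change to the planned analyses.
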